9.2 SETTING

9.2.1 Observation Period

This will be a non-interventional study using existing Optum EHR data for the period of July 1, 2011 through March 31, 2017. Patients with a written prescription for linagliptin will be identified during an identification period starting on January 1, 2012 and ending on September 30, 2016. The date of the first written prescription for linagliptin during the identification period will be designated as the index date without a prior prescription for linagliptin in the pre-index period.

Baseline characteristics will be evaluated during the 180-day period prior to the index date (pre-index period) and on the index date. Outcomes will be assessed during the 180-day period following the index date (follow-up period). A diagram of the study observation period is provided in Figure 1.

Figure 1. Study Observation Period

9.2.2 Inclusion Criteria

To be included in the study sample, patients must meet all of the following criteria:

- ≥ 1 written prescription for linagliptin (Tradjenta[®], Jentaducto[®], or Jentaducto XR[®]) in the EHR data during the identification period (medication codes for index medications in Table 1 of [Annex 1, Appendix B](#))
- ≥ 40 years of age based on the year of the index date
- First active date in the EHR is ≥ 180 days prior to the index date
- ≥ 1 diagnosis code representing T2DM in the EHR data during the 180-day pre-index period or on the index date (diagnosis codes in Annex 1, Appendix A)
- ≥ 1 HbA1c value during the 180-day pre-index period or on the index date
- ≥ 1 HbA1c value 60 to 180 days after the index date

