	
be defined based on eGFR as: <30 ml/min/1.73m², 30 to 44 ml/min/1.73m², 45 to 59 ml/min/1.73m², 60 to 89 ml/min/1.73m², and ≥ 90 ml/min/1.73m².
 
The secondary study objectives are to:
 
• Compare change in HbA1c among adults with T2DM within 60 to 180 days following initiation of linagliptin across pre-defined age and renal function categories.• Compare the proportion of adults with T2DM who achieve HbA1c $< 7.0\%$ within 60 to 180 days following initiation of linagliptin across the pre-defined age and renal function categories.
--	---

Study design:	Non-interventional study based on existing data
Population:	Patients with T2DM newly initiated on linagliptin, in the Optum electronic health record (EHR) database, aged 40 and older, and with HbA1c values during the both the 180 days before and the 60 to 180 days after starting linagliptin
Variables:	
Outcomes:
 
 • Primary: Change in HbA1c within 60 to 180 days after initiation of linagliptin • Secondary: HbA1c goal (< 7.0%) attainment during the 60 to 180 days after initiation of linagliptin 
Covariates:
 
 • Age categories: 40 to 54 years, 55 to 64 years, 65 to 74 years, and ≥ 75 years • Sex • Race • Ethnicity • Geographic region • Pre-index comorbidity score • Pre-index HbA1c value • Pre-index renal function categories (based on the eGFR): <30 ml/min/1.73m², 30 to 44 ml/min/1.73m², 45 to 59 ml/min/1.73m², 60 to 89 ml/min/1.73m², and ≥ 90 ml/min/1.73m²
Data sources:	Optum electronic health record (EHR) data

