9.2.3 Exclusion Criteria

Patients will be excluded from the study sample if they have any of the following:

- ≥ 1 written prescription, medication administration or medication history record for linagliptin or other DPP-4 inhibitor in the EHR data during the 180-day pre-index period (medication codes for DPP-4 inhibitors in Table 2 of [Annex 1, Appendix B](#))
- ≥ 1 written prescription or medication administration for a new antihyperglycemic medication other than linagliptin on the index date

New antihyperglycemic medication will be defined as a written prescription or medication administration for any antihyperglycemic medication that was not present in the patient's written prescription, medication administration, or medication history records during the 180-day pre-index period. Medication codes for antihyperglycemic medications are shown in Tables 2 through 13 of [Annex 1, Appendix B](#). Individual antihyperglycemic medications will be distinguished by generic name using the column labelled "Medication Name" in Tables 2 through 13. Combination products containing two generic ingredients will be considered as two distinct antihyperglycemic medications.

Note: This exclusion criterion is designed to exclude patients from the study sample if they start a new antihyperglycemic medication other than linagliptin on the index date. Patients that start a new antihyperglycemic medication in the follow-up period will not be removed from the study sample to avoid creating a biased sample. Addition of a new antihyperglycemic medication during follow-up will be evaluated through the sensitivity analysis described in Section 9.7.4.4. While we will be capturing additions of new therapies, discontinuation of linagliptin is not able to be accurately measured in electronic record data. The electronic record data capture prescriptions written by a prescriber, but it is not possible to know if patients received and adhered to their medication and there are no structured data fields to identify if and when a medication was discontinued by the patient or the provider.

- ≥ 1 diagnosis code or procedure code representing renal transplant, solid organ transplant, or bone marrow transplant in the EHR data during the 180-day pre-index period or on the index date (diagnosis and procedure codes in [Annex 1, Appendix A](#))

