Fourth, in contrast to many real world evidence studies, this study does not have an active comparator. Since all other DPP4 inhibitors require dose adjustment for declining renal function, a comparator study to show similar/different effectiveness would be difficult to design to be able to account for all the patient factors that contribute to medication distribution, elimination and dosing and likely would require an inordinately large data base.

Fifth, due to the descriptive nature of this study, multiple different comparisons are being conducted to evaluate change in HbA1c by age, renal function, and race categories. We have not adjusted our p values for multiplicity but we may perform post hoc adjustments if requested by reviewers during the publication process.

Finally, the findings from this study are expected to have limitations that are common to analyses conducted with retrospective EHR data. The possibility of misclassification exists in all studies that rely on retrospective data. Evidence of conditions and events that are based on reported diagnosis codes or procedure codes may not reflect confirmed diagnoses. While EHR data capture prescriptions written by a prescriber, it is not possible to know if patients received and adhered to their medication and there are no structured data fields to identify if and when a medication was discontinued by the patient or the provider. The EHR database does not include the entire medical chart for the patient, which raises the possibility of missing data. Unlike claims data, EHR data do not contain eligibility information and continuous eligibility is not able to be assessed. Services provided to the patient by facilities and providers outside of the healthcare systems providing EHR data to Optum will not be captured although this is not expected to be a major limitation in this study because the primary outcome, HbA1c, is likely to be measured by the same provider who wrote the patient's prescription for linagliptin. However, there may be circumstances where a patient may receive care that falls outside of their provider's electronic record system such as being treated at an out of network hospital.

Despite these limitations, EHR data are a powerful source of data for the examination of health outcomes in the "real world" setting away from the highly controlled environment of

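### Section 9.2.2 requires no record in the 180 days before index, so a patient with an empty window can enter as a new initiator on index-day data alone

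*Combined protocol and SAP*

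**What the plan says.** Three inclusion criteria in Section 9.2.2 govern what must be known before index:

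- Look-back: "First active date in the EHR is ≥ 180 days prior to the index date".
- Diagnosis: "≥ 1 diagnosis code representing T2DM in the EHR data during the 180-day pre-index period or on the index date".
- Baseline HbA1c: "≥ 1 HbA1c value during the 180-day pre-index period or on the index date".

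The Abstract describes the population more narrowly, as patients "with HbA1c values during the both the 180 days before and the 60 to 180 days after starting linagliptin", and does not mention the index date.

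New use is defined in Section 9.2.3 by the absence of any prescription, administration or medication history record "for linagliptin or other DPP-4 inhibitor in the EHR data during the 180-day pre-index period". The index date is not named there, although it is named in the transplant and malignancy exclusions of the same section. A further exclusion applies to patients with "≥ 1 written prescription or medication administration for a new antihyperglycemic medication other than linagliptin on the index date". A drug counts as new if it has no record in the 180-day window. Section 9.2.4 allows this exclusion to be waived, with a flag, if it costs too many patients.

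Under Section 9.3.3.2, the Quan-Charlson score is built from codes present in the window or on the index date. Section 9.7.3 puts that score and individual comorbidities in the model. Section 9.9 states that "EHR data do not contain eligibility information and continuous eligibility is not able to be assessed". Section 9.12 concedes that incomplete history in the 180 days may misclassify baseline characteristics, and says the limitations will be acknowledged in the report.

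**The concern.** A first active date is a single point in time. It does not show that the patient was under observation in the 180 days that matter, and the plan reads absence of a record in those days as absence of the drug or condition.

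Two things are at stake. First, a patient already taking linagliptin from a source outside the database could be counted as an initiator. The baseline HbA1c would then be measured on drug, and the change would be pulled towards zero. Second, comorbidity would be under-recorded for patients whose window is empty, which weakens the adjustment in the multivariable model.

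The study compares HbA1c change across age and renal groups. If empty windows are more common in some groups than in others, either error could create or hide a difference between groups.

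**Working it through.** **1. Can a patient with an empty window enter?** Take a patient with one contact before day -180, nothing from day -180 to day -1, and an index-day visit with a T2DM code, an HbA1c and a linagliptin prescription. The age criterion and the follow-up HbA1c are assumed to be met.

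| Rule | Result with an empty window |
|---|---|
| First active date (9.2.2) | Met by the old contact |
| T2DM code (9.2.2) | Met on the index day |
| Baseline HbA1c (9.2.2) | Met on the index day; not met under the Abstract's wording |
| DPP-4 inhibitor washout (9.2.3) | Passed, since there are no records to search |
| Transplant, malignancy (9.2.3) | Judged on index-day codes alone |
| Other new drug on index day (9.2.3) | Excluded if any other glucose-lowering drug is written or given that day; otherwise passes |
| Quan-Charlson, comorbid conditions (9.3.3.2) | Index-day codes alone |
| Pre-index therapy (9.3.3.2) | No pre-index records to draw on |

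So entry is possible. It is limited mainly to patients for whom linagliptin is the only glucose-lowering drug written that day, unless the 9.2.4 waiver applies.

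**2. Do the documents give the share affected?** No. Section 9.7.1 gives 16,566 / 38,868 = 42.6% with both HbA1c values, and 15,130 / 16,566 = 91.3% of those with a serum creatinine. Neither figure counts patients without a record in the window.

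**3. Illustrative size.** All three inputs are assumptions: 5 to 15% of a group have an empty window, 20 to 50% of those are already users, and a user's change is about 0 instead of about -0.6. The 0.6 is close to the placebo-adjusted -0.64 and -0.77 cited in Section 7.

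Dilution of the mean = share empty × share already users × 0.6

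- Low: 0.05 × 0.20 × 0.6 = 0.006
- High: 0.15 × 0.50 × 0.6 = 0.045

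The high value is 0.045 / 0.5 = 9% of the difference used for sizing in Section 9.5.

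For a comparison of two groups, only the difference in dilution matters. Suppose the high value falls wholly in one group, with 2,500 patients in each (the lower bound that 9.7.1 gives for the smallest age cell) and the SDs of 9.5:

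- SD 1.2: SE = 1.2 × √(2/2500) = 0.034, and 0.045 / 0.034 = 1.3 SE
- SD 1.5: SE = 1.5 × √(2/2500) = 0.042, and 0.045 / 0.042 = 1.1 SE

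**4. Sample size.** The plan's 92 and 143 per group (difference 0.5, SD 1.2 or 1.5, 80% power, two-sided 0.05) reproduce. The two-sample t-test calculation gives 91.39, rounded up to 92, and 142.25, rounded up to 143. The point does not depend on them, but they show the cost of turning the flag into a criterion:

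| Assumed share removed | Of 16,566 | Of 2,500 |
|---|---|---|
| 5% | 15,738 | 2,375 |
| 10% | 14,909 | 2,250 |
| 20% | 13,253 | 2,000 |
| 30% | 11,596 | 1,750 |

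The smallest age cell stays above 143 until 1 - 143/2500 = 94% are removed. No counts are given by eGFR category, so the same check cannot be made there.

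**5. Is the window always covered by data?** Data start on 1 July 2011 and indexing starts on 1 January 2012 (9.2.1), 184 days later. Day -180 to day -1 is therefore available for every index date.

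**The case against.** The strongest reply is that few such patients will enter and that the limitation is already stated.

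- The rule on other new drugs works against them. With an empty window, every other glucose-lowering drug written that day is new, so a transferring patient whose whole regimen is rewritten is excluded. Because combination products count as two medications, an index prescription for a linagliptin/metformin product could, on that wording, exclude as well. This stands, and it narrows the problem. The 9.2.4 waiver could undo it, although those patients would be flagged.
- The washout also searches medication history, not only local prescriptions. That helps only if the entry is dated inside the window, because the rule does not name the index date.
- Anyone with an HbA1c before the index day has a record in the window. The feasibility count in 9.7.1 describes HbA1c in the six months before index. Read literally, nobody in that count has an empty window. But 9.2.2 is the operative criterion and it is wider.
- Sections 9.9 and 9.12 disclose the general limitation. This stands too, so the gap is not one of disclosure. What is missing is a check: continuous eligibility cannot be assessed, but recorded activity can be.
- One record in the window does not prove that prescribing was fully observed. This is true, and the flag therefore identifies the clearest cases only.

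A reader might infer that these patients have no record at all before the index visit, or that they enter with no comorbidity. Neither follows. The look-back criterion requires activity at least 180 days earlier, and index-day codes count towards the Quan-Charlson score and the comorbid conditions.

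**Conclusion.** The gap is real but narrow. As written, 9.2.2 admits patients with no record in the 180 days before index. Their new-user status then rests on absent data, and their comorbidity covariates on a single day's codes.

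Neither the share affected nor the bias can be derived from the documents. The range of 0.006 to 0.045 HbA1c percentage points rests wholly on the assumed shares and the assumed 0.6 effect. It is small against 0.5. At its upper end, confined to one group, it is about one standard error of an age-group comparison. The documents do not show that prevalent users are in the cohort, or that empty windows differ by age or renal function. A reader should not conclude that the comparisons are biased, only that the plan has no means of finding out. The issue concerns validity, not power for the age comparisons. A cheap sensitivity analysis is the proportionate response.

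**What to change.** Add to Sections 9.3.3.2 and 9.7.3: flag patients with no recorded encounter, prescription, diagnosis or laboratory result from day -180 to day -1, excluding the index date. Report their number and share by age group and by eGFR group, including the group whose eGFR is not available. Repeat the main HbA1c tables and the multivariable model without them.

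The interval should match the 180 days over which the washout and covariates are measured. A one-year interval would not serve, because a single contact on day -300 would satisfy it and still leave the 180-day window empty.

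The alternative is to make such a record an inclusion criterion in 9.2.2. In either case, reconcile the Abstract with 9.2.2 on whether an index-day HbA1c counts as baseline.

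Cost: the flag needs one derived variable and one re-run on data already extracted, and the main analysis loses nobody. The criterion loses some patients, probably a modest number, to be shown in the attrition counts. The age cells can bear it. The eGFR cells should be counted first, because their sizes are not given and 9.7.1 already expects that some may be too small.

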- ≥ 1 diagnosis code representing malignancy in the EHR data during the 180-day pre-index period or on the index date (diagnosis codes in Annex 1, Appendix A)

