9.9 LIMITATIONS OF THE RESEARCH METHODS

This study has several limitations inherent to its non-interventional study design. There may be baseline differences in the different age and renal function categories. In randomized clinical trials, these differences are mitigated by randomization. Among the important considerations is if there are substantial differences in baseline HbA1c. It is well known that the change from HbA1c is a function of baseline HbA1c, ie, the higher the baseline HbA1c, the greater the change from baseline even with comparable doses of the glucose lowering medication. This observation has been confirmed by Esposito et al (22) in their analyses of several DPP4 inhibitors.

Second, we have selected a follow up window of 6 months rather than a longer window e.g. up to 1 year. Maximal effectiveness is usually achieved by 6 months, although in randomized controlled trials HbA1c values may be lower at later time points. This limitation is balanced against the observation that medication persistence at 6 months will likely be

better than at 12 months and the fact that we wish to maximize the numbers of patients in each of the age and renal function cells.

Third, duration of T2DM is likely to be longer in patients with lower renal function. Increased duration of diabetes is also associated with greater reductions in beta cell function. Since one of the mechanisms of DPP4 inhibitor medications is to increase GLP-1 mediated insulin secretion, reduced renal function could theoretically be associated with diminished glycemic effectiveness. If the current study supports this observation, this will confound the claim of comparable glycemic effectiveness across the range of renal function, but it will be an important observation for the management of T2DM patients. Lajra et al reported on a retrospective analysis of 202 patients from two separate trials in which patients with > 10 years of diabetes were randomized to linagliptin 5 mg (n = 122) or placebo (n = 80)(15). The placebo adjusted mean difference in HbA1c was -0.66% (95% CI -0.85 to -0.38). No direct comparisons were made with shorter duration of diabetes. However, these data suggest that differences in duration of diabetes are unlikely to have a major effect on the data obtained in the current proposal.

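### One T2DM code admits a patient and nothing identifies those who also carry type 1 diabetes codes; the likely bias is small, and counting and removing them in a sensitivity analysis is cheap

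*Combined protocol and SAP*

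**What the plan says.** Section 9.2.2 requires at least one "diagnosis code representing T2DM in the EHR data during the 180-day pre-index period or on the index date". The other entry rules are a linagliptin prescription, an age of at least "40 years of age based on the year of the index date", a first active EHR date at least 180 days before index, and HbA1c values before and after index.

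Section 9.2.3 opens with "Patients will be excluded from the study sample if they have any of the following" and lists four items, each triggered by one record:
- a "written prescription, medication administration or medication history record for linagliptin or other DPP-4 inhibitor in the EHR data during the 180-day pre-index period";
- a "written prescription or medication administration for a new antihyperglycemic medication other than linagliptin on the index date";
- a "diagnosis code or procedure code representing renal transplant, solid organ transplant, or bone marrow transplant in the EHR data";
- a "diagnosis code representing malignancy in the EHR data during the 180-day pre-index period or on the index date".

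None concerns type 1 diabetes or conflicting diabetes codes. Insulin already in use does not trigger the second item, and Section 9.3.3.2 records basal, bolus and mixed insulin as pre-index therapy.

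The covariates in Section 9.7.3 are age, sex, race, ethnicity, region, pre-index HbA1c, eGFR category, comorbidity score and the top 20 comorbidities. Diabetes type, diabetes duration and pre-index antihyperglycemic therapy are not named. The sensitivity analysis mentioned in Section 9.2.3 concerns drugs added during follow-up. Sections 9.9 and 9.12 acknowledge code misclassification in general terms, without naming type 1 diabetes.

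On mechanism, Section 9.9 states that "one of the mechanisms of DPP4 inhibitor medications is to increase GLP-1 mediated insulin secretion", and reasons that lower beta-cell function could in theory reduce the glycemic effect.

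**The concern.** All objectives in Section 8 concern adults with T2DM. As written, a patient coded type 1 many times and type 2 once in the window meets the diagnosis criterion, and no later step finds that patient.

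Section 9.1 asks whether effectiveness is comparable across age and renal function groups. If patients with type 1 codes respond less and are more common in some groups than in others, part of a between-group difference would reflect who was admitted rather than age or renal function. The study has no comparator (Section 9.9) in which such a component could cancel, and Section 9.7.3 reports p-values unadjusted for multiplicity. An equal share in every group would create no false difference, but it would shrink a true one.

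**Working it through.** **Inputs from the protocol**
- Study size (Section 9.5): difference 0.5, SD 1.2 or 1.5, 80% power, two-sided alpha 0.05; stated n = 92 or 143 per group.
- Drug effect in T2DM, E (Section 7): placebo-adjusted 0.64 and 0.77 HbA1c points at 24 weeks, from two trials in patients aged 70 or older.
- Cell sizes (Section 9.7.1): more than 2,500 aged 40 to 54 and more than 3,000 aged over 75, taken here as 2,500 and 3,000.

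**Inputs assumed**
- Shares of patients with type 1 diabetes in two groups, p1 and p2: not in the documents; gaps of 2 to 10 percentage points are shown.
- Drug effect in these patients: zero, the extreme case of no response.
- Change unrelated to the drug: the same in both kinds of patient.

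**Step 1. The plan's own figure.** The two-sample t-test calculation gives 91.39 and 142.25, which round up to the stated 92 and 143. The normal approximation gives 91 and 142. The study size reproduces and is not in dispute.

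**Step 2. False difference from unequal shares.** Bias = E × (p2 − p1).

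| Shares | E = 0.64 | E = 0.77 |
|---|---|---|
| 1% vs 3% | 0.64 × 0.02 = 0.013 | 0.77 × 0.02 = 0.015 |
| 2% vs 5% | 0.64 × 0.03 = 0.019 | 0.77 × 0.03 = 0.023 |
| 2% vs 10% | 0.64 × 0.08 = 0.051 | 0.77 × 0.08 = 0.062 |
| 0% vs 10% | 0.64 × 0.10 = 0.064 | 0.77 × 0.10 = 0.077 |

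The first two rows are about 3% to 5% of the 0.5 target (0.0128/0.5 = 2.6%; 0.0231/0.5 = 4.6%). A false difference of 0.5 would need shares 0.5/0.77 = 65 to 0.5/0.64 = 78 percentage points apart.

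**Step 3. Could it reach nominal significance?** Threshold = 1.96 × SD × √(1/2,500 + 1/3,000).
- SD 1.2: 1.96 × 1.2 × 0.02708 = 0.064.
- SD 1.5: 1.96 × 1.5 × 0.02708 = 0.080.

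Gaps of 2 to 3 points stay well below both thresholds. A gap of 10 points (0.064 to 0.077) reaches the first and falls just short of the second. The feasibility steps in Section 9.7.1 mention no T2DM code and do not apply the 60-day lower limit for the follow-up HbA1c, so final cells may be smaller and the thresholds higher.

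**Step 4. Equal shares, true difference 0.5.** The observed difference is 0.5 × (1 − p).
- p = 5%: 0.475; normal-approximation power at 92 or 143 per group is about 76% to 77%.
- p = 10%: 0.450; power is about 72%.

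This matters only for groups near the minimum size. The two age cells with stated counts are far larger; counts by eGFR group are not given.

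**The case against.** The strongest case against is that the effect is immaterial and the premise partly borrowed. A T2DM code, a linagliptin prescription and age 40 or older together already limit the share. Insulin use will be visible by stratum, because pre-index measures are reported by stratum (Section 9.7.2). Misclassification is disclosed. The 0.64 and 0.77 are placebo-adjusted, whereas this study measures uncontrolled change, so even the direction of bias rests on assumption. All of this stands and is why the point ranks low. Still, disclosure does not count or remove these patients, and insulin use does not establish diabetes type.

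The T2DM code list assigned to Appendix A is not in the supplied text. It would not change the point: an inclusion list cannot remove a patient who also has type 1 codes. The separate analysis plan that holds the table shells was not supplied either, so an analysis described only there cannot be ruled out.

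Three stronger readings are tempting but unsupported:
- *The drug cannot work in these patients.* Section 9.9 calls insulin secretion one mechanism among others. Its argument concerns T2DM duration, and it concludes that duration is unlikely to matter much.
- *These patients cluster in the youngest or lowest-eGFR groups.* That is plausible, but the documents give no share, overall or by group.
- *A small cell of young patients with eGFR below 30 would be badly distorted.* Section 9.7.2 stratifies by age and by renal function separately. The cross-classification appears only as an example in the study-size text and as a potential category in the feasibility counts.

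**Conclusion.** The gap is real: one T2DM code suffices, and no criterion, named covariate or sensitivity analysis in the supplied documents addresses patients who also carry type 1 codes. The consequence is probably small, about 0.01 to 0.02 HbA1c points for share differences of 2 to 3 percentage points. Only a difference near 10 points (0.06 to 0.08) would come close to nominal significance at the feasibility cell sizes, and even that is at most about 15% of the 0.5 target (0.077/0.5).

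These sizes rest on no drug effect in type 1 patients, on trial effects standing in for the T2DM response, and on assumed shares. The effect on HbA1c goal attainment cannot be sized from the documents. The point is a cheap improvement and does not call the study's main conclusions into question.

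**What to change.** In Section 9.2.3, using the same 180-day pre-index period and index date as the diagnosis-based criteria:
1. Add a type 1 diabetes code list to Appendix A and flag patients with any such code.
2. Report the number flagged by age and by eGFR stratum.
3. Prespecify that the stratum comparisons of HbA1c change and goal attainment are repeated without flagged patients. Alternatively, exclude them outright, with one line in the attrition table.

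A rule that compares counts of type 1 and type 2 codes over all available records is less suitable. The length of EHR history and visit frequency vary between patients, and Section 9.9 notes that continuous eligibility cannot be assessed, so misclassification could then itself differ by age and renal function.

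The cost is one code list and one repeated set of tables, from data already in hand and by the same kind of code check used for transplant and malignancy. The downside is that a few true T2DM patients with a miscoded visit drop out of that analysis. Fixing the rule before results are seen avoids a post hoc choice.
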